attention control group. Caregivers will be recruited through 19 community organizations (serving rural communities in 17 states). Primary outcomes will be caregiver stress and depression symptoms. We hypothesize that stress scores and depression symptoms will be significantly improved at 12 months in the intervention group versus control group. We will also identify key strengths (facilitators) and weaknesses (barriers) of workshop implementation. We will use the RE-AIM implementation framework and a mixed methods approach to identify implementation characteristics pertinent to both caregivers and rural community organizations.

If the *Building Better Caregivers* workshop is proven to be effective, this research has the potential to open new research horizons, particularly on how to reach and effectively support isolated dementia caregivers in rural areas with an intervention that is scalable, even in low-resourced settings. If the workshop can achieve its goals with rural dementia caregivers, some of those most isolated, it would also be expected to be scalable in other low-resourced settings (e.g., in urban or suburban environments).

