## 8.2 HYPOTHESIS: Describe the hypothesis or what the study hopes to prove (Help Text updated 9/13):

We propose to conduct a hybrid effectiveness-implementation randomized controlled trial of the *Building Better Caregivers* online self-management workshop among rural caregivers of partners with Alzheimer's disease or other forms of dementia. We hypothesize that stress scores and depression symptoms will be significantly improved at 12 months in the intervention vs. control group (Aim 1). We also will identify the key strengths (facilitators) and weaknesses (barriers) of workshop implementation to characterize its potential to achieve widespread, community-based, real-world implementation in rural America (Aim 2).

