## 8.4 DESIGN: Briefly describe the study design (e.g., observational, interventional, randomized, placebo-controlled, blinded, cross-over, cross-sectional, longitudinal, pharmacokinetic, etc.):

We will recruit 640 rural dementia caregiver adults through 19 community organizations (serving rural communities in 17 states to implement a randomized, attention controlled clinical trial. Caregivers will be randomized to receive the online intervention (workshop) group or attention control group. The online workshops will be facilitated by trained caregivers who will lead workshops. We will assess both primary and secondary outcomes at baseline, 1.5 months (post intervention), 6 and 12 months, with the main intervention group comparison being at 12 months. Interested control group caregivers also will be offered the workshop after the trial is completed.

Using mixed methods approach we will identify implementation characteristics pertinent to caregivers, identify patterns of experience across all workshop participants via analysis of implementation questions embedded in trial surveys administered to all participants. To more deeply understand these experiences, we will interview a sample of 60 caregivers—15 per US region (West, Midwest, Northeast, South).

To determine implementation characteristics pertinent to community organizations, we will collect data from our partner community organizations on experiences of barriers and facilitators. Analyses will compare and contrast characteristics within and between organizations. Findings will

identify essential elements of workshop implementation that should be incorporated into future implementation efforts. Findings on effective and ineffective strategies will inform the implementation of other online programs for rural, caregiver, and Alzheimer's disease populations.

**8.5 BACKGROUND AND SIGNIFICANCE: Briefly provide the background and significance of this study (e.g. why is this study needed) (space limit: one half page):**

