b. **Attention control group.** Participants will receive written materials on dementia and caregiver resources and two brief phone calls of 15-30 minutes apiece by research staff. Caregivers in the attention control group will be offered the online workshop after the 12 month trial is completed if they so desire. The written materials and phone call guides are still under development and will be submitted to the IRB for review as a modification request.

**For control group fidelity purposes.** Phone calls will be recorded. [name] and the research coordinator will evaluate recordings using a fidelity assessment instrument. Staff who stray from the phone call protocol will receive immediate remedial training. If an RA strays from the protocol again, he/she will be removed from making phone calls. At the outset of the trial, fidelity assessment will occur approximately every 4-5 calls to assure fidelity patterns are quickly established and reinforced. Subsequent checks will occur every 10-12 calls.

5. **Assessments:** Data will be collected at baseline, 1.5 months (post intervention), 6 months, and 12 months. Data will be collected through online surveys completed by caregivers and conducted at baseline, post-intervention (1.5 months), and 6, and 12 months using the secure REDCap application. Assessments are expected to be 20 minutes each. Participants will be given the option to complete surveys by mail or phone interview.

a. **Baseline** questions will ask about caregiver and PWD demographic information (e.g., age, gender, race/ethnicity, education); caregiving relationship to PWD (e.g., spouse, child), and resources participants are accessing (e.g., paid in-home care). Baseline questions also will identify caregiver and partner chronic conditions (e.g., using the Charlson comorbidity index), partner need for assistance with ADLs and IADLs, and dementia characteristics (e.g., diagnosis, length of diagnosis, degree of impairment, presence of behavioral symptoms). Caregiver (CG) stress level (Stress visual numeric scale), CG depression symptoms (PHQ-8 score), Self-efficacy (Revised Scale for Caregiver Self-efficacy), Burden (Zarit Burden Inventory), Strain (Caregiver Strain Index), Global health score, and Healthcare utilization items.

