**8.26 STATISTICAL METHODS: Briefly summarize the methods and types of analyses that will be performed:**

**Aim 1 Data Analysis Methods.**

**Descriptive analyses.** Caregiver and caregiver-reported partner socio-demographic characteristics, chronic conditions, and health utilization outcomes will be summarized as means ( $\pm$ SD), frequencies, percentages, and 95% confidence intervals at baseline and 1.5, 6, and 12 months. The distributions of covariates at baseline will be checked for balance between the two groups with histograms and/or boxplots.

**Primary analyses.** Primary analyses will compare caregiver stress (stress score) and depression symptoms (PHQ-8 score) between intervention and control groups over time with respective linear mixed effects models. Linear mixed effects models use all available observations in the data, assume data are missing at random, and provide an intention-to-treat analysis. Models will include group, time, and (group\*time) interaction terms as fixed effects and community organizations and subjects as random effects to account for the correlation within organizations and subjects due to measurements over time. Covariates with imbalanced distributions between the two groups will also be included in the models to control for potential confounding. The (group\*time) interaction term will be used to evaluate if the two groups differ in outcomes over time. The study is powered to allow 30% loss to follow up. To assess for potential differential withdrawal between groups, comparisons of withdrawal rates and time to withdrawal will be performed. Models based on a potential outcome framework will be used to assess treatment effect while accounting for noncompliance and missing data and to examine potential treatment mechanisms/pathways via intermediate variables (such as social support, self-efficacy, caregiving skills). Multiple imputation based on reasonable assumptions on mechanisms of missing data will be used to perform sensitivity analyses.

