## 10.0 Sample Size and Eligibility Criteria

**10.1 ENROLLMENT TARGET: How many people will you enroll:**

If there are multiple participant groups, indicate how many people will be in each group:

**For Aim 1 Sample for RCT.** We will recruit 640 rural dementia caregiver adults through 19 community organizations (serving rural communities in 17 states to implement a randomized, attention controlled clinical trial. 320 in the intervention group and 320 in the control group for a total of n=640.

**For Aim 2 Sample for In-depth Interviews.** We will randomly select a sub-set of intervention group caregivers for semi-structured telephone interviews regarding workshop implementation characteristics. We will sample for caregivers (n=60 total) from all US regions (n=15 per region—West, Midwest, South, Northeast).

**For Aim 1 and Aim 2 Sample for Learning Collaborative.** 19 community organizations (serving rural communities in 17 states) will have at most 2 representatives participating in the Learning Collaborative (n=2\*19=38).

**10.3 SAMPLE SIZE JUSTIFICATION: Explain how and why the number of people was chosen. For multi-site studies, this is referring to the number that will be enrolled across all sites:**

The study is powered on the co-primary outcome with the lowest effect size in pilot studies—the PHQ-8 depression symptoms score (effect size 0.27). We will use a recruitment target of 640 participants. We assume 30% loss to follow-up, thus expecting 448 caregivers (224 per group) will complete the study at 12 months. This sample size of 448 will allow us to detect a PHQ-8 effect size of 0.265 with a power of 0.8 at a significance level of 0.05 (two-sided). The effect size of 0.265 corresponds to a 1.5 difference in PHQ-8 score (range 0-24) between groups assuming a common standard deviation of 5.6. We also will have the power to detect a 1.4 difference in the co-primary outcome of stress score (range 0-10) between the two groups.

If we encounter problems meeting trial enrollment benchmarks, we will work with local organizations and others to find alternative recruitment strategies such as health system-based patient portals or recruitment through national caregiver discussion groups. We also can add additional partner organizations after the start of the study.

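### Section 8.26 tests the group-by-time term without selecting the 12-month contrast that the hypothesis names, and leaves baseline-score adjustment to observed imbalance

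*Combined protocol and SAP*

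**What the plan says.** All references are to the combined protocol and SAP unless the 2019 power memo is named.

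- **Hypothesis.** Section 8.2: "We hypothesize that stress scores and depression symptoms will be significantly improved at 12 months in the intervention vs. control group". The project summary in section 4.1 says the same.
- **Main comparison.** Section 8.4 lists assessments at baseline, 1.5, 6 and 12 months, "with the main intervention group comparison being at 12 months".
- **Sample size.** Section 10.3 assumes 30% loss, "thus expecting 448 caregivers (224 per group) will complete the study at 12 months", and states power 0.80 for a PHQ-8 effect size of 0.265, two-sided 0.05.
- **Primary test.** Section 8.26 fits linear mixed models with group, time and their interaction as fixed effects, and organization and subject as random effects. The "interaction term will be used to evaluate if the two groups differ in outcomes over time". It names no visit, and it does not say whether time is categorical or continuous, or whether baseline is an outcome row.
- **Covariates.** Section 8.26: "Covariates with imbalanced distributions between the two groups will also be included in the models to control for potential confounding". Balance is to be judged from histograms or boxplots. The baseline outcome score is not named, although section 8.10 lists stress and PHQ-8 in the baseline survey.
- **2019 power memo.** It adds randomization ratio as a categorical covariate in the analysis model. It names neither a 12-month contrast nor baseline adjustment, and section 8.26 does not list the ratio term.

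**The concern.** With four visits, a group-by-time term can be tested in at least three ways: jointly on 3 df with time categorical, as a difference in linear slopes, or as the single 12-month coefficient. They answer different questions. The joint test can be significant because of a benefit just after the 6-week workshop that has gone by 12 months. The slope test depends on the shape of the effect and loses power when the benefit comes early and then holds. Only the 12-month contrast tests the Aim 1 hypothesis. Two analysts following section 8.26 could report different primary p-values from the same data.

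The second issue is precision. If baseline is an outcome row with a free group term, the 12-month coefficient is a difference in change scores. That is valid, but it is less precise than a baseline-adjusted comparison whenever the baseline correlation is below 1. An adjustment rule triggered by observed imbalance does not secure the gain in advance.

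**Working it through.** **Inputs from section 10.3:** d = 0.265 SD, two-sided 0.05, 224 completers per arm. **Assumptions:** equal correlation r between any two visits (the documents give none; 0.5 is used below, then a range), unit variance at each visit, no organization effect, and the effect profiles shown.

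**Step 1. The plan's own figure.** I = 224 × 224 / 448 = 112. A plain two-group comparison has noncentrality λ = d² × I = 0.070225 × 112 = 7.87, giving power 0.80. Also 448 / 0.70 = 640. The stated figures reproduce, and they describe a single-time-point difference.

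**Step 2. 3-df joint test.** The three change-from-baseline differences δ have covariance (1 − r)(I₃ + J₃)/I, where I₃ is the identity and J₃ the all-ones matrix. Hence λ = [I/(1 − r)] × [Σδ² − (Σδ)²/4], and at r = 0.5, I/(1 − r) = 224.
- 1.5 months only (d, 0, 0): 224 × 0.75 × 0.070225 = 11.80, rejection 0.83.
- Sustained (d, d, d): 3d² − 9d²/4 is also 0.75d², so again 11.80 and 0.83.
- Linear growth (d/8, d/2, d): 224 × 0.6055 × 0.070225 = 9.52, power 0.74.
- Fading (0.265, 0.13, 0): 224 × (0.087125 − 0.039006) = 10.78, rejection 0.80.

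**Step 3. Slope test.** Times 0, 1.5, 6 and 12 have mean 4.875 and Sxx = 87.1875. The slope variance is (1 − r)/(I × Sxx) = 1/19,530.
- Sustained: slope 0.265 × 4.875 / 87.1875 = 0.01482; λ = 4.29; power 0.54.
- Linear growth: slope 0.265 / 12 = 0.02208; λ = 9.52; power 0.87.
- 1.5 months only: slope 0.265 × (1.5 − 4.875) / 87.1875 = −0.01026; λ = 2.06; rejection 0.30.

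**Step 4. 12-month contrast.** Variance is 2(1 − r)/I with a free baseline and (1 − r²)/I with baseline adjustment.
- Free: λ = 0.070225 × 112 / 1 = 7.87, power 0.80.
- Adjusted: λ = 0.070225 × 112 / 0.75 = 10.49, power 0.90.
- No effect at 12 months: both reject at 5%.

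**Rejection rates, 224 per arm, r = 0.4 / 0.5 / 0.6**

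| True profile | 3-df joint | Slope | 12-month, free | 12-month, adjusted |
|---|---|---|---|---|
| 1.5 months only | 0.75 / 0.83 / 0.91 | 0.26 / 0.30 / 0.36 | 0.05 | 0.05 |
| Sustained | 0.75 / 0.83 / 0.91 | 0.47 / 0.54 / 0.64 | 0.73 / 0.80 / 0.88 | 0.86 / 0.90 / 0.94 |
| Linear growth | 0.65 / 0.74 / 0.84 | 0.80 / 0.87 / 0.93 | 0.73 / 0.80 / 0.88 | 0.86 / 0.90 / 0.94 |

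A simulation of 4,000 trials per profile at r = 0.5 agreed to within 0.01.

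**Step 5. All available observations.** Section 8.26 analyses partial follow-up too. With 320 randomized per arm and 10% lost at random before each follow-up visit (an assumed pattern), generalized least squares over the dropout patterns gives, for r = 0.4 / 0.5 / 0.6:
- 12-month power 0.77 / 0.84 / 0.91 free and 0.87 / 0.91 / 0.95 adjusted;
- adjusted-to-free variance ratio 0.765 / 0.806 / 0.846, against 0.70 / 0.75 / 0.80 in completers (where it equals (1 + r)/2);
- joint-test rejection 0.85 / 0.91 / 0.96 for an effect at 1.5 months only.

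Moving all the loss before 1.5 months, or all of it after 6 months, changes the r = 0.5 power only to 0.83–0.85 free and 0.90–0.91 adjusted.

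**Step 6. The 2019 allocation.** With 480 completers and r = 0.5, the 12-month power, free then adjusted, is:
- all 1:1 (I = 240 × 240 / 480 = 120): 0.83 and 0.92;
- all 2:1 (I = 320 × 160 / 480 = 106.7): 0.78 and 0.885;
- all 3:1 (I = 360 × 120 / 480 = 90): 0.71 and 0.83.

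**The case against.** The strongest reply is that the time point is already fixed. Sections 4.1, 8.2 and 8.4 all say 12 months, section 10.3 counts 12-month completers, and nothing in the documents mentions a joint test or a slope. Read together, the 12-month coefficient is the natural primary comparison. That is fair, and the gap is one of wording rather than two declared, conflicting estimands. It remains a gap, because section 8.26 is where the decision rule is stated and it selects no contrast.

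Section 8.26 is also a form field asking for a brief summary, and the DSMB charter refers to a Manual of Procedures that is not among the documents. The detail may be there, so this point concerns the wording of 8.26 only.

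On baseline adjustment, the free-baseline contrast is valid and meets 0.80 at r = 0.5. The size of the gain depends on an unknown r. In completers power rises from 0.66 to 0.84 at r = 0.3, but only from 0.95 to 0.975 at r = 0.7 and from 0.993 to 0.997 at r = 0.8. This stands: adjustment is an improvement, not a correction.

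Finally, the harm is conditional. The high rejection rates need both the joint-test reading and an effect gone by 12 months. For a sustained effect at r = 0.5 the joint test (0.83) does no worse than the free 12-month contrast (0.80). The issue is what a positive result would mean, not lost power in every case.

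**Conclusion.** The concern holds and should be fixed. Section 8.26 does not tie its primary test to the 12-month hypothesis, and the alternatives that its wording permits can give a different answer. For a benefit confined to 1.5 months, the joint test rejects 75–91% of the time in completers, against 5% for the 12-month contrast. For a sustained benefit, the slope test has power 0.47–0.64 against 0.73–0.88. Unconditional baseline adjustment cuts the variance of the 12-month contrast by 20–30% in completers and by about 15–24% with all available data.

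These ranges rest on r from 0.4 to 0.6, equal correlations, no organization effect, the assumed effect profiles and dropout patterns, and 1:1 allocation. The baseline gain has the same direction under the 2:1 and 3:1 ratios. The wording gap does not depend on r. No power shortfall in the 2019 plan is claimed; the memo states 0.82 for the chosen varying-ratio plan, for a partial correlation of 0.13.

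**What to change.** Amend section 8.26, before outcome data by arm are examined, to state that:

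- time is categorical;
- the primary test for each co-primary outcome is the single-df group contrast at 12 months from the mixed model, with its 95% confidence interval;
- the baseline score of that outcome is always adjusted for, whatever the observed imbalance. Use one of two forms, not both: baseline kept as an outcome row with a common mean across arms within randomization-ratio stratum, or post-baseline outcomes only with a baseline-by-time covariate;
- the joint interaction test and the 1.5- and 6-month contrasts are supportive;
- randomization ratio enters as a categorical term, as the 2019 memo already promises (a consistency update).

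The change needs the same data and software and no extra participants. The only cost is a text amendment, which the DSMB would see because its charter covers proposed protocol changes.

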Statistical Power Considerations in Building Better Caregiver Study

Study: R01 AG057855-01
PI: [name]
Date: 11 August 2019
NCT04428112

This document is a response to the DSMB recommendation: "The study team should provide a written explanation and revision to account for the changes in power calculations, particularly regarding drop-out rates."

Summary from study team. The statistical power consideration was revised based upon updated information on the challenges in the recruitment and retention provided by the study team. The study team, which includes the study biostatistician, has selected the randomization approach "*Varying (flexible) randomization ratio (1:1, 2:1, 3:1)*" described below based on changes in expected retention and power calculations also described below.

The original statistical power consideration was based on 1:1 randomization to treatment and control. Assuming 70% retention rate, 448 caregivers at the end of the study will allow us to detect an effect size of 0.265 in the primary outcome PHQ-8 depression symptoms score with a power of 0.80 at a significance level of 0.05 (two-sided). The effect size of 0.265 corresponds to about 1.5 difference in PHQ-8 score (range 0-24) between groups assuming a common standard deviation of 5.6 (Lorig K, Thompson-Gallagher D, Traylor L, et al. Building Better Caregivers: a pilot online support workshop for family caregivers of cognitively impaired adults. *Journal of Applied Gerontology*. 2012;31:423-437.)

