The recruitment and retention challenge came to light based on new information from the accumulated experience with the VA BBC workshop, which has enrolled over 5,000 Veteran caregivers. Unpublished data made available to the study team demonstrates that if caregivers' respective assigned workshops do not start within 2 weeks, they quickly lose interest and do *not* attend the workshops. This new data prompted the current study team to reconsider the recruitment, randomization, and retention plan. The study team recognized that if study enrollment could not accrue fast enough to fill both a workshop group and attention control group within a 2-week period (i.e., total of 54 participants per 2-week period) at 1:1 randomization, then retention would drop precipitously similar to what has been documented for some VA caregivers. The new data suggest that the original 1:1 randomization plan may lead to a retention rate of 50%, and 320 caregivers at the end of study will provide a power of 0.66 to detect the same effect size of 0.265.

The revised statistical power consideration was based on randomization with ratios of 1:1, 2:1 or 3:1 to treatment and control, depending on the actual recruitment process of participants within each 2-week period of recruitment. The 2:1 and 3:1 randomizations are expected to help with the recruitment and retention.

Fixed randomization ratio (2:1, 3:1)

Assuming that a fixed ratio of 2:1 will be used in randomization and the retention rate will increase from 50% to 75%, then the sample size of 480 caregivers (320 in treatment and 160 in control) at the end of the study will provide us a power of 0.78 to detect the same effect size of 0.265.

Assuming that a fixed ratio of 3:1 will be used in randomization and the retention rate will increase from 50% to 75%, then the sample size of 480 caregivers (360 in treatment and 120 in control) at the end of the study will provide us a power of 0.71 to detect the same effect size of 0.265.

Varying (flexible) randomization ratio (1:1, 2:1, 3:1)

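### The claim of 0.80 power with 30% loss (sections 8.26 and 10.3) is correct only for fixed 1:1 allocation and was not updated when varying 1:1, 2:1 or 3:1 randomisation was selected

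*Combined protocol and SAP*

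**What the plan says.** **Combined protocol and SAP.** Section 8.26 (Aim 1, primary analyses) states: "The study is powered to allow 30% loss to follow up". That sentence gives only the loss rate; the rest is in section 10. Section 10.1 sets enrolment at "320 in the intervention group and 320 in the control group for a total of n=640". Section 10.3 continues: "We assume 30% loss to follow-up, thus expecting 448 caregivers (224 per group) will complete the study at 12 months", and then "This sample size of 448 will allow us to detect a PHQ-8 effect size of 0.265 with a power of 0.8", two-sided at 0.05. It ties the effect size to the outcome scale: "The effect size of 0.265 corresponds to a 1.5 difference in PHQ-8 score (range 0-24) between groups assuming a common standard deviation of 5.6". Sections 4.1 and 8.3 repeat 320 per group.

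**Power memo (the document named Protocol, 11 August 2019).** The memo answers a DSMB request to explain and revise the power calculations, drop-out in particular. It states: "The study team, which includes the study biostatistician, has selected the randomization approach" with a varying 1:1, 2:1 or 3:1 ratio, chosen by how many caregivers enrol in each two-week period. It adds: "The revised statistical power consideration was based on randomization with ratios of 1:1, 2:1 or 3:1 to treatment and control". Retention is assumed to be 75%, so 480 of 640 complete. For the selected plan the memo gives power 0.82 for a partial correlation of 0.13, with the ratio as a categorical covariate. At d = 0.265 and 75% retention it gives 0.78 for fixed 2:1 and 0.71 for fixed 3:1. It gives no figure for 30% loss under unequal or varying ratios.

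**The concern.** The two documents describe one trial with different arm sizes, completer numbers and loss rates. The power statement in sections 8.26 and 10.3 depends on equal arms. For a fixed total, unequal allocation lowers power, and 448 completers at 1:1 only just reach 0.80, so there is no margin to absorb it.

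The DSMB asked specifically about retention. A reader of section 8.26 would conclude that 30% loss is tolerable at the planned power. Under the selected allocation that is not assured, and how far power falls depends on how many participants are randomised in 2:1 and 3:1 periods.

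**Working it through.** **Inputs.** d = 0.265 and two-sided alpha 0.05 (section 10.3 and memo); 640 enrolled (both documents); 448 completers at 30% loss (section 10.3); 480 at 25% loss (memo); treatment share p = 1/2, 2/3 or 3/4 for the three ratios (memo).

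**Formula.** For two groups with N completers in total and share p in treatment, the noncentrality is λ = d × √(N·p·(1−p)). Power is approximately Φ(λ − 1.96). The noncentral t was used as a cross-check. The product p(1−p) is 0.25 at 1:1, 0.2222 at 2:1 and 0.1875 at 3:1.

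**Reproducing the documents' own figures.**
- 1:1, N = 448: λ = 0.265 × √112 = 2.804; power 0.801 (stated 0.80).
- 2:1, N = 480: λ = 0.265 × √106.67 = 2.737; power 0.781 (stated 0.78).
- 3:1, N = 480: λ = 0.265 × √90 = 2.514; power 0.710 (stated 0.71).

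All three agree, so the method matches the one behind the plan.

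**The stated 30% loss under each allowed ratio, with the memo's 25% loss alongside.**

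| All periods at | N = 448: λ | Power (noncentral t) | N = 480: λ | Power (noncentral t) |
|---|---|---|---|---|
| 1:1 | 2.804 | 0.801 (0.799) | 2.903 | 0.827 (0.826) |
| 2:1 | 2.644 | 0.753 (0.751) | 2.737 | 0.781 (0.780) |
| 3:1 | 2.429 | 0.680 (0.679) | 2.514 | 0.710 (0.708) |

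**Detectable difference.** With 448 completers, the d detectable with 0.80 power is (1.960 + 0.842)/√(N·p·(1−p)): 0.265 at 1:1, 0.281 at 2:1 and 0.306 at 3:1. Multiplied by the assumed SD of 5.6, these are about 1.5, 1.6 and 1.7 PHQ-8 points.

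**A small share of 2:1.** Suppose 5% of the 448 completers come from 2:1 periods and the rest from 1:1 (an illustration, not a figure from the documents). The average p(1−p) is 0.95 × 0.25 + 0.05 × 0.2222 = 0.2486, and power by the noncentral t is 0.797. At 10% it is 0.795 and at 20% it is 0.790.

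**Does the memo's 0.82 cover the gap?** A partial correlation r corresponds to d = [r/√(1−r²)]/√(p(1−p)). With r = 0.13 the numerator is 0.1311. Dividing by 0.5, 0.4714 and 0.4330 gives d of 0.262 at 1:1, 0.278 at 2:1 and 0.303 at 3:1. Under unequal allocation the memo's target is therefore a larger effect than 0.265, and its 0.82 also assumes 25% loss. With 448 completers the same target has power of about 0.79.

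**The case against.** **The stated 0.80 is not an arithmetic error.** Correct: 224 per group gives 0.80. The fault is one of consistency between documents.

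**The combined document may simply be older.** A reader might infer that two rival plans are in force. The documents do not support that. The memo labels 1:1 with 70% retention as original and the varying ratio as revised. The combined document has its trial registration number pending and its DSMB members not yet approved (section 13.4), and it cites over 3,000 VA caregivers where the memo cites over 5,000. Its date is not shown, so the order is an inference, but every cue points the same way. The better reading is an application not brought into line with a later decision.

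**Neither document pairs 30% loss with unequal ratios.** True. The memo expects the varying ratio to raise retention to 75%, so the 0.68–0.80 range applies only if retention is the 70% that section 8.26 says the study can bear. But that is what section 8.26 claims, so it is fair to test it under the selected allocation.

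**A few 2:1 periods do little harm.** This also stands. It is tempting to say that the claim fails as soon as any period departs from 1:1. With 5% of completers at 2:1, power still rounds to 0.80. Nor do the documents support a single figure for the expected mix; an equal split across ratios, for example, would be a reviewer's assumption.

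**The memo already discloses the cost of unequal allocation, and its own target loses little.** It does report 0.78 and 0.71 at d = 0.265, and 448 completers give about 0.79 for the 0.13 correlation. But sections 8.26 and 10.3 rest on d = 0.265, and the memo's own figures for that effect under fixed 2:1 and 3:1 are below 0.80 even with 25% loss.

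**Conclusion.** The point holds as an inconsistency with a measurable effect. Power of 0.80 at d = 0.265 with 30% loss is right for fixed 1:1 allocation and is not assured under the varying ratio that the team selected. With 448 completers the shortfall runs from nothing (all periods 1:1) through about 5 percentage points (all 2:1) to about 12 (all 3:1). With the memo's 480 completers, power exceeds 0.80 at 1:1 and falls below it if all periods run 2:1 or 3:1.

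The ends of each range require every period to use the same ratio; the realised value lies between and cannot be fixed from the documents. The figures use a simple two-group comparison at 12 months, as the documents' own figures do. The planned mixed model, with repeated measures and organisation effects, could move the absolute values. This should be corrected, but it does not show that the trial is too small or the selected design unsound.

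**What to change.** In sections 4.1, 8.3 and 10.1 of the combined document, replace the fixed 320 and 320 with the selected varying ratio, keeping the total of 640. In section 10.3, do the same for the 224 per group, and adopt one retention assumption consistent with the memo. In sections 8.26 and 10.3, replace the unqualified statement about 30% loss with power at d = 0.265 as a range over the allowed ratios: about 0.71–0.83 at 75% retention (480 completers) and about 0.68–0.80 at 70% (448 completers). If a figure for one particular mix of ratios is added, label the mix as an assumption. If the 0.82 is carried over, state its target (partial correlation 0.13, 25% loss) and the d it corresponds to at each ratio, so that it is not read as power for d = 0.265.

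The cost is text edits and a less favourable stated power. Enrolment, design and analysis do not change.
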